#### **Self-Administered Measures (Appendix 5a/5b):**

- Demographics and Health Behaviors
- Fear of Recurrence Inventory--Severity Subscale
- Insomnia Severity Index
- PROMIS – Fatigue Scale – Short Form 8a
- SF-36 Health Survey
- Impact of Events Scale-Revised
- Satisfaction with Medical/Mental Health services

#### **Interviewer Administered Measures and Chart Review (Appendix 6):**

NCORP component research staff will administer the following forms (see Appendices) by telephone (or in person if participant is in clinic) and enter the data on the study website as the data are collected.

These forms are to be interviewer-administered whether the contact is by telephone or in person.

The PHQ-9 and GAD-7 should have no missing data.

- PHQ-9 (administer only if it has been >30 days since screening to reassess eligibility)
- GAD-7 (administer only if it has been >30 days since screening to reassess eligibility)
- Charlson Comorbidity Index
- Cornell Services Index
- Current Medication Use

Chart Review:

- Initial Cancer Diagnosis and Treatment Form
- Additional Malignancy Diagnosis and Treatment Form
- Cancer Relapse/Recurrence Form

### **7.5 Participant Enrollment and Randomization**

The electronic participant enrollment form (Appendix 7) will be completed on the day of randomization in the Telehealth study website. The subject should not be randomized and enrollment form completed until the subject is ready to start the intervention. Review the Appendix 5a/5b (Baseline Self-Report Measures) for completeness before randomization. Once the participant is randomized, the study timeline begins. A participant will not be considered enrolled if they are not randomized to a study arm. Following randomization, the Randomization Form should be completed (Appendix 8).

### **7.6 Evaluation During Study Intervention**

**Weeks 1-12:**

- **High Intensity Week 1/Low Intensity Week 2:** The Expectancy Rating Scale and instructions (Appendix 10a/b) will only be mailed to participants who are randomized to either the Low Intensity or the High Intensity intervention groups. Participants are to complete this Expectancy Rating Scale after they have completed Chapter 1 of the Cognitive Behavior Therapy Workbook.

- Enhanced Usual Care participants will not be mailed the Expectancy Rating Letter or Scale.
- Enhanced Usual Care participants will be mailed a “Thank You” letter at baseline (Support Document 6).
- Stepped-Care Telehealth (High Intensity) Progress Notes (Appendix 16)/Session Information Form (session completed Y/N) (Entered by therapist or NCORP component research staff on study website within 48 hours of therapy or check-in sessions)
- Telephone Script/Manual for Low Intensity Bi-Weekly (every two weeks) Check-In Call Form (Appendix 14).
- Implementation costs (tracking logs) (Appendix 24)

**Week 7:** (visit must be completed between Week 6 and Week 11)

NCORP component research staff will administer the following mid-intervention assessments by telephone and enter in the study website (Appendix 11).

- PHQ-9
- GAD-7
- Current Medication Use (Update)
- Adverse Event Ascertainment Form
- Mid-intervention letter mailed to Enhanced Usual Care participants only (Support Document 6).

**7.7 Evaluation at Completion of Study Intervention – Week 13 (could occur weeks 13-15 only for High Intensity Participants):** (visit must be completed between Week 12 and Week 15)

**Self-Administered Measures (Appendix 12a/b):**

Participants will be mailed the following self-report post-intervention measures with a request that they be returned within two weeks.

- Fear of Recurrence Inventory--Severity Subscale
- Insomnia Severity Index
- PROMIS Fatigue Scale- Short Form 8a
- SF-36 Health Survey
- Impact of Events Scale – Revised
- Client Satisfaction Questionnaire
- Working Alliance Inventory-Participant (high-intensity participants only)
- Expectancy Rating Scale (low intensity and high intensity participants only)

**Interviewer Administered Measures and Chart Review (Appendix 13):**

NCORP component research staff will administer the following post-intervention measures by telephone and enter on the study website:

- PHQ-9
- GAD-7
- Cornell Services Index
- Current Medication Use (Update)
- Adverse Event Ascertainment Form

Chart Review:

- Cancer Relapse/Recurrence Form

After all therapy sessions with each participant have been completed, the therapist will complete the Working Alliance Inventory-Therapist form (Appendix 17). The Working Alliance Inventory is a process measure to evaluate the potential impact of the telehealth intervention on the therapist-participant relationship.

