### **5.3 Treatment Fidelity**

For the purposes of the study, therapists (who may or may not be employees at NCORP component sites) are considered to be research therapists and will contract (or subcontract) with the study to directly provide services for the research grant. As part of the contract, research therapists will be required to meet quality metrics including the audiotaping of psychotherapy sessions to ensure treatment fidelity. All therapy sessions will be audiotaped, and 8% of psychotherapy sessions (1 session per randomized participant) will be randomly selected for review (not live) by [name] using a measure of therapist adherence (Appendix 18) and competence developed and used by Stanley and colleagues (Stanley et al., 1996; Stanley et al., 2003). This measure assesses both the competence and adherence of the therapist in the delivery of the specific skills of the intervention (e.g., progressive muscle relaxation, problem solving, etc.) as well as an overall rating of therapist competence and adherence. Data suggest high internal consistency ( $\alpha = .91\text{-.94}$ ) and greater variability in ratings attributed to clinicians (29%) than raters (9%), suggesting good reliability of the instruments (personal communication, [name]; see Appendix 18 for a copy of this measure.)

Local site staff that are part of the research team and are responsible for making check-in calls with study participants will be audio-taped for adherence to study protocol and competence. All check-in calls will be audiotaped and 16% of calls (1 session per participant) will be randomly selected for review (not live) by [name] using a measure of adherence and competence developed for this study (see Appendix 19 for a copy of this measure.) [name] will meet via telephone with the research staff whose ratings indicate difficulties in intervention delivery.

Therapists (CBT)/research staff (check-in calls) who do not demonstrate competency (competency score  $< 6$ ) will receive additional training until competency is demonstrated. [name] will meet with therapists on a regular basis to discuss cases, review therapist adherence and competence ratings, and answer questions regarding protocol administration. Any areas of nonadherence will be reviewed, and the therapist will review any difficulties in intervention delivery.

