## 7. CLINICAL EVALUATIONS AND PROCEDURES

### 7.1 Intervention Description

Participants with moderate anxiety and depressive symptoms will be randomized to either the low-intensity stepped-care telehealth or the EUC control. Participants with severe symptoms will be randomized to either the high-intensity stepped-care telehealth intervention or the EUC control. Therapists participating in the trial must meet the following requirements: a Master's or doctoral degree in counseling, marriage and family therapy, psychology, or social work; licensed as an independent mental health provider in California, Georgia, Illinois, Kansas, Michigan, Minnesota, Missouri, New Mexico, North Carolina, North Dakota, South Carolina, Virginia, Tennessee, or Wisconsin; and experience with cognitive-behavioral therapy. Experience working with oncology patients/survivors is preferred. Therapists will attend a 1.5-day training that will cover information on study design, anxiety and depression in cancer survivors, principles of cognitive-behavioral therapy, delivery of the intervention, and use of the web-based data-entry system. NCORP sites and/or components may nominate therapists for participation, but are not required to identify a therapist to participate. The Wake Forest study team will identify a participating therapist for each state.

Low Intensity Stepped-care Telehealth: The low-intensity stepped-care telehealth group will consist of a self-guided CBT workbook (15 minutes daily to read and complete exercises/homework) and biweekly (every two weeks) check-in calls (5-10 minutes) from an NCORP component research staff person to assess changes in symptom severity/immediate need for psychiatric treatment and provide minimal support. Check-in calls are expected to be completed within +/- 2 days of the window specified in the Telehealth website; however, check-in calls up to +/- 1 week of the window are permitted.

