High Intensity Stepped-care Telehealth: The high-intensity stepped-care telehealth group will consist of the CBT workbook (15 minutes daily to complete exercises/homework), plus psychotherapy delivered by telephone with a licensed therapist (45 minute sessions weekly). If participant is randomized to the High

Intensity Arm, the therapist will make at least one attempt to schedule the participant's first therapy session within 2 weeks of the date of notification via email.

Consistent with the ASCO guidelines, the Wake Forest NCORP Research Base staff will mail a professionally prepared and IRB approved CBT workbook to participants and participants will have 12 weekly therapy sessions with the study therapist. The study therapist will be a licensed mental health provider (e.g., licensed clinical social worker, marriage and family therapist, licensed professional counselor, psychologist). Onsite or phone training is provided for all participating therapists. Training will include the use of the workbook, formal didactic presentations, readings, and role-plays. All study therapists will receive regular (at least monthly) study supervision from [name]. There will be at least one trained therapist for each state in the U.S. that has any participating sites. Each week, the participant will receive one 45-minute telephone session and one workbook chapter. The sessions will supplement the participant's understanding of anxiety, depression, and distress management techniques and include a review of the daily workbook exercises to assure understanding and maximize application in daily life.

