Enhanced Usual Care. At the time of randomization, EUC participants will receive: (1) information about referrals/resources (Sample Resource Sheet) in their local area, including support groups and mental health providers (Appendix 20 and Support Document 9); (2) information about written self-help resources (several readily available published workbooks) for anxiety and depressive symptoms; and (3) a copy of the National Cancer Institute publication entitled "Facing Forward: Life after Cancer Treatment." This publication can be viewed at the following web link: <https://www.cancer.gov/publications/patient-education/life-after-treatment.pdf>. Site staff should contact the NCORP Research Base site coordinator who will ship a copy of the booklet to each EUC participant within two weeks of randomization. It addresses the topics of follow up medical care, physical changes, body changes and intimacy, feelings, and social and work relationships. Upon completion of the Week 13 post-intervention assessment battery, the Wake Forest NCORP Research Base staff will send a black and white 2-sided copy of the CBT workbook to participants in EUC (same workbook provided to participants in the low-intensity and high-intensity intervention groups). In addition, the EUC randomization script can be used to help explain EUC to participants who are randomized to the EUC condition.

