### 8.2 Secondary Endpoints

#### 8.2.1. Depression and Anxiety Measures

The **PHQ-9** is a self-report measure of DSM-IV symptoms of Major Depressive Disorder. Participants rate how often they have experienced nine symptoms over the past 2 weeks on a scale of 0 (not at all) to 3 (nearly every day). Responses are summed, with higher scores indicating greater depressive symptomatology. It has demonstrated good reliability and validity. The traditional cutoff for the PHQ-9 is a score  $\geq 10$ . However, ASCO guidelines recommend using a score  $\geq 8$ , based on a study of cancer outpatients and a meta-analysis of use of the PHQ-9 for identifying depression in cancer patients.

The **GAD-7** is a self-report measure of DSM-IV symptoms of GAD. Participants rate 7 questions on a scale of 0 (not at all) to 3 (nearly every day); one additional question assesses the interference of these symptoms with functioning. The first 7 questions are summed to create a total score. It has been validated for use in the general population and in primary care. The GAD-7 has demonstrated good sensitivity (89%) and specificity (82%) in identifying GAD diagnoses when using a cut point of 10. It also has good internal consistency (alphas = 0.89-0.92) and test-retest reliability (intraclass correlation = .83).

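### The Week 7 and Week 13 PHQ-9 and GAD-7 interviews fall to the same unmasked site staff pool that makes the low-intensity support calls, leaving the low-intensity effect open to interviewer bias of unknown size and direction

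*Combined protocol and SAP*

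**What the plan says.** **Outcome interviews.** Section 7.6 (Week 7) says "NCORP component research staff will administer the following mid-intervention assessments by telephone and enter in the study website", and Section 7.7 (Week 13) says "NCORP component research staff will administer the following post-intervention measures by telephone and enter on the study website". The PHQ-9 and GAD-7 head both lists, for all arms.

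**Low-intensity contact.** Section 7.1 describes two-weekly calls "from an NCORP component research staff person to assess changes in symptom severity/immediate need for psychiatric treatment and provide minimal support". Section 5.3 places them with "Local site staff that are part of the research team and are responsible for making check-in calls with study participants". The Study Parameter Table schedules six calls (weeks 2, 4, 6, 8, 10 and 12). It lists them under the same site-staff heading as the Week 7 and Week 13 interviews.

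**The other arms.** High intensity adds to the workbook "psychotherapy delivered by telephone with a licensed therapist", and the therapist is not assigned the outcome interviews. EUC receives printed material and referral information.

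**Knowledge of allocation.** Site staff complete the randomization form and send a Week 7 letter to EUC participants only. Section 7.1 adds that "the EUC randomization script can be used to help explain EUC to participants who are randomized to the EUC condition".

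**Nature of the instruments.** Section 8.2.1 says that the PHQ-9 "is a self-report measure of DSM-IV symptoms of Major Depressive Disorder", and it describes the GAD-7 likewise. For the fear-of-recurrence, insomnia, fatigue, quality-of-life and cancer-distress scales, Section 7.7 says: "Participants will be mailed the following self-report post-intervention measures with a request that they be returned within two weeks".

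**The concern.** In one arm only, the person who reads out the symptom questions may be the person who has been phoning with support. On the nominal schedule, three support calls precede the Week 7 interview and all six precede the Week 13 interview. A participant may answer a familiar caller differently from a stranger, and an interviewer who knows the arm may prompt differently.

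Baseline adjustment does not deal with this. The baseline scores come from screening, before allocation and before any support call. The staff term in the Section 13.5 mixed model does not deal with it either. That term identifies the therapist or the check-in caller, not the person who collected the outcome, and it has no evident value for EUC participants.

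What is at stake is the planning information. Section 13.3 bases the sample size partly on estimating effect sizes for a larger trial, and Section 13.8 says the intervention effects will be used for planning. Section 13.5 also compares each stepped-care group with EUC on the combined outcome, so a shift confined to low intensity would enter that comparison undiluted.

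**Working it through.** **1. Can the roles overlap, and where?**

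| Group | Who provides intervention contact | Who interviews at Weeks 7 and 13 | Overlap possible? |
|---|---|---|---|
| Low intensity | NCORP component research staff | NCORP component research staff | Yes |
| High intensity | Licensed therapist | NCORP component research staff | No |
| EUC | No support calls (Section 7.1, Study Parameter Table) | NCORP component research staff | No |

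The protocol body contains no masking of interviewers and no rule that caller and interviewer must differ. Lack of masking affects every group; the overlap of roles affects one.

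**2. The plan's own precision (Section 13.3).** Inputs: 45 per group, 20% dropout, SD of change 5.8 (PHQ-9) and 4.2 (GAD-7).
- Completers: 45 × 0.80 = 36 per group.
- Half-width of the 95% interval: 1.96 × √(2/36) = 0.462 SD.
- PHQ-9: 0.462 × 5.8 = 2.68 points. GAD-7: 0.462 × 4.2 = 1.94 points.

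This reproduces the stated ±0.46 SD, 2.7 points and 1.9 points. The half-width covers sampling error only.

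**3. Precision for low intensity versus EUC.** Section 13.2 plans 50 participants in the moderate strata with equal allocation, so 25 per group, or 25 × 0.80 = 20 after dropout.
- Half-width: 1.96 × √(2/20) = 0.620 SD, which is 3.59 PHQ-9 points and 2.60 GAD-7 points.

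**4. Illustration of a shift.** The documents give no figure. Assume a shift of 0.1 to 0.3 SD, in either direction, in interviews done by the participant's own caller, and assume at first that all low-intensity interviews are of that kind.
- Low intensity versus EUC: 0.1 × 5.8 = 0.58 to 0.3 × 5.8 = 1.74 PHQ-9 points; 0.1 × 4.2 = 0.42 to 0.3 × 4.2 = 1.26 GAD-7 points. As a share of the half-width: 0.1/0.620 = 16% to 0.3/0.620 = 48%.
- Pooled stepped care versus EUC: 25 of the 45 stepped-care participants are low intensity, so multiply by 25/45 = 0.556. This gives 0.32 to 0.97 PHQ-9 points and 0.23 to 0.70 GAD-7 points. As a share of the half-width: 0.0556/0.462 = 12% to 0.167/0.462 = 36%.
- If only half of the low-intensity interviews were done by the participant's own caller, the figures halve. The pooled PHQ-9 shift would be 0.16 to 0.48 points.

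**The case against.** The case for leaving the plan alone has real weight.

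- **No shared individual is shown.** The documents name a staff category, not a person. A reader might infer that each low-intensity participant is interviewed by their own caller. The text does not say so; it only fails to prevent it.
- **The direction is open.** It is tempting to conclude that participants will report fewer symptoms to someone who has helped them, so that the bias favours low intensity. Nothing in the documents supports that. Familiarity could also increase disclosure and work against low intensity.
- **The contact is thin.** Calls are scripted, last 5 to 10 minutes (30 to 60 minutes over six calls) and are recorded, with a sample reviewed. EUC participants also know this staff pool from screening, consent, baseline and Week 7.
- **The contrast with the other outcomes is not clean.** A reader might think that every other outcome is on paper and only these two are oral. Section 7.2 offers non-responders the questionnaires by telephone, and the Cornell Services Index, which feeds the cost analysis, is also interviewed at Week 13.
- **Interviewing is defensible.** The items have fixed responses, and interviewing suits the requirement that baseline scores be complete and the 48-hour data entry.
- **The text may be incomplete.** The Study Parameter Table refers to Appendix 26 for details of these interviews, and that appendix was not available. Section 12.4 also mentions check-in calls for EUC, which conflicts with Section 7.1 and the table.

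These points limit how strongly the concern can be put. They do not remove it: fixed responses restrict the interviewer's scoring but not how the participant chooses to answer. Without a record of who interviewed, the trial could not examine the question afterwards.

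**Conclusion.** The point holds as a structural exposure to bias, not as a demonstrated bias. The same unmasked staff pool makes the low-intensity support calls and collects the PHQ-9 and GAD-7 at both follow-up times. Nothing in the protocol body keeps the two roles apart for a given participant, and only low-intensity participants can be affected by the overlap.

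The low-intensity versus EUC contrast bears any shift in full and the pooled effect bears 25/45 of it. The illustrated sizes (up to 1.7 PHQ-9 points, or 1.0 pooled) rest on an unsourced 0.1 to 0.3 SD and on complete overlap, so partial overlap reduces them proportionally.

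A reader might go further and conclude that the trial's main result is compromised. It is not: the primary endpoint is feasibility, and Section 13.8 says the effect analyses are not meant to demonstrate efficacy. The reason to act is that the effect sizes will be carried into the next design and the safeguard is cheap.

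**What to change.** 1. In Sections 7.6 and 7.7, state that a participant's check-in caller does not do that participant's Week 7 or Week 13 PHQ-9 and GAD-7 interview when another trained staff member is available at the component, and that items are read verbatim.
2. Record the interviewer's ID at both visits and whether the interviewer was the participant's caller. The caller's identity is already needed for the Section 13.5 model, so the second item can be derived.
3. In Section 13.5, add a descriptive sensitivity analysis that repeats the low-intensity versus EUC comparison without own-caller interviews. Say plainly that the remaining low-intensity subset is small (at most about 20 completers), not randomized, and likely to be related to component size.
4. Reconcile the Section 12.4 reference to EUC check-in calls with Section 7.1 and the Study Parameter Table. If Appendix 26 already separates the roles, say so in the protocol body.

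A mailed, self-completed PHQ-9 and GAD-7 at Week 13 is not recommended. It would be set against a baseline taken by interview, and the plan has no step for handling answers to the suicidal-ideation item on a returned form.

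The cost is one data field, one descriptive analysis and some scheduling. Scheduling will be hardest at small components, since Section 7.2 expects fewer than 10 participants per state, and there the first step may have little effect. No extra staff are needed, and neither the sample size nor the planned precision changes.

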**7.8 End of Study**

Upon completion of study visits, the Participant Completion Letter (Support Document 3) and the Resource Sheet (Support Document 9) will be mailed to participants in the Low Intensity and High Intensity groups.

**7.9 Methods for Clinical Procedures**

The Study Parameter Table (below) indicates the timing, mode of administration, and person who administers every aspect of the study.

## Study Parameter Table

	Recruitment/ Chart Review	Pre-Screen	Verbal Consent	Full Screen	Full Informed Consent	Baseline	Enrollment/ Randomization (wk0)	Weeks 1-13			Post Week 13
								Wk1 or 2	W7	W13	
NCORP Component Site Staff Responsibility											
Mail Recruitment Documentation*	As needed										---
Pre-Visit Form (Appx 2)	X										---
Pre-Screening Form (Appx 3)*		X a									---
Abbreviated Verbal Consent			X a								---
Screening Form (Appx 4)*				X a							---
Full Informed Consent					X a						---
Baseline Self-Report Letter and Measures (Appxs 5a+b)*						X a					---
Baseline Interviewer-Administered Measures and Chart Review (Appx 6)*							X a				---
Letter to Ineligible Participants (SD 2)		As Needed									---
Enrollment Form (Appx 7)							X				---
Randomization Form (Appx 8)							X b				---
EUC Randomization*							X		X		EUC
Expectancy Rating Scale and Letter  (Appxs 10a+b)							X				LISC/ HISC
Low Intensity Check-In Call Form (Appx 14)								Biweekly (wks 2/4/6/8/10/12)			LISC
Upload audio recordings								Biweekly (wks 2/4/6/8/10/12)			LISC
Week 7 Mid-Assessment Interviewer-Administered Measures (Appx 11)*									X		All
Week 13 Self-Report Letter and Measures (Appxs 12a+b)*										X	All
Week 13 Interviewer-Administered Measures (Appx 13)*										X c	All
Participant Completion Letter (SD 3)/Resource Sheet (SD 9)										X	LISC/ HISC
Participant Change Status Form (Appx 23)								As Needed			All
Adverse Event Form (Appx 22)		As Needed									All
Crisis Protocol Event Form (Appx 21)		As Needed									All
Tracking Log (Appx 24)		To be completed for each attempted contact and actual contact									All
Wake Forest Research Base Responsibility											
EUC Randomization*							X				EUC
Investigator adherence rating forms (Appx 18 and 19)*								As needed			LISC/ HISC
Mail Recorder							As needed				LISC/ HISC
Mail CBT Booklet							X				LISC/ HISC
Mail CBT Booklet										X	EUC
Study Therapist Responsibility											
Weekly Therapist activities (Appxs 15-17) recordings*								Weekly (wks 1-13)			HISC
Tracking log		To be completed for each attempted contact and actual contact									HISC

Abbreviations: Appx=Appendix, EUC=Enhanced Usual Care, HISC=High-Intensity Stepped-Care Arm, LISC=Low-Intensity Stepped-Care Arm

\* See appendix 26 for details

a If participant is being seen in person, all of these steps can occur during one appointment

b Randomization should happen within 30 days of the full screen. If not, full screen (appx 4) will need to be re-administered

c For participants in the HISC arm, week 13 measures should be completed after the intervention is finished (could be weeks 13-15)

**Note:** Regarding potential participant burden, estimated times to complete study measures are as follows: pre-screen (5-10 minutes); screen (up to 20 minutes); participant measures at baseline and Week 13 (30-60 minutes); participant measures at Week 7 (5 minutes)

**Note:** See the Telehealth website for specific windows of when data should be collected post-randomization for each participant. The PHQ-9 and GAD-7 must be entered into the Telehealth website within 48 hours of administration. All other assessments should be entered within 14 days of the date assessments are completed unless otherwise specified.

